After completing the foregoing, submit the HSRP with supporting documentation via email to the IRB Mailbox:
[contact]

For questions, email:

[name], Research Compliance Coordinator, [contact]

[name], JD, Research Compliance and Export Control Officer, [contact]

Researchers

	Name	Email (use TAMUCC email)	College	Category	Category (Other)
PI	R		Nursing & Health Sciences	Other	
Co-PI (1)					
Co-PI (2)					
Co-PI (3)					
Co-PI (4)					
Co-PI (5)					

Overview

A. Research Classification: Research Project Other: N/A

For guidance, see Determination of Level of Review at the end of the HSRP.

B. Level of Review: Expedited (1)

C. Indicate whether external funding applies. No Award Start Date: N/A Maestro #: N/A

D. Title: Effects of Cranial Electrotherapy Stimulation on Psychological Distress and Maternal Functioning in New Mothers during the Postpartum Period.

E. Research Anticipated Start Date: Upon IRB approval. F. Estimated Completion Date:

Purpose and Objective

A. Describe the purpose of the research **in layman's terms.**

The purpose of this study is to evaluate the effects of cranial electrotherapy stimulation (CES) on anxiety, insomnia, depression, and maternal functioning in first time new mothers following childbirth.

B. Describe the objective(s) and/or research questions **in layman's terms.**

The primary objective of this study is to investigate the effect of cranial electrotherapy stimulation (CES) on anxiety in new mothers following childbirth. The secondary objectives are to: (1) determine the effects of CES on depression and insomnia; (2) explore the effect of CES on maternal functioning in new mothers following childbirth, and (3) to examine if items 1 & 2 on the 14 item Hamilton Anxiety Rating Scale (HAM-A14) perform well as a screening test for anxiety. Please see the enclosed Instrument Description document for detailed information related to this scale.

Participants; Recruitment

Participants

A. Indicate whether the following populations will be specifically targeted for inclusion in the research. Each category must be answered.

Adults over the age of 18 (able to legally consent)	Y  N 	Prisoners (adults or juveniles)	Y  N 

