Adults over the age of 18 (unable to legally consent)	Y  N 	Participants whose first language is not English	Y  N 

Minors under the age of 18	Y 	N 	Students enrolled in a researcher's course(s)	Y 	N 
Pregnant Women, fetuses, and/or neonates Note: Projects including this vulnerable population are generally health care/ medical studies specifically targeting research of pregnant women, fetuses, and/or neonates. Pregnant women can be included in projects if all inclusion criteria is met and a specific exclusion is not part of the project design. Select "No" unless the project specifically involves the inclusion of pregnant women, fetuses, and/or neonates.	Y 	N 	Employees under the direct supervision of a researcher	Y 	N 

B. Describe the criteria to determine who is included or excluded in the final participant population (e.g., minimum age, grade range, physical characteristics, learning characteristics, professional criteria, etc).

Instruments: See attached document entitled "Instrument Description" for detailed information related to this the scales referenced in this protocol.

- The Hamilton Anxiety Rating Scale (HAM-A14)
- Hamilton Depression Rating Scale17 (HAM-D17)
- The Pittsburgh Sleep Quality Index (PSQI19)
- The Insomnia Severity Index (ISI7)
- The Barkin Index of Maternal Functions (BIMF20)

Screening and Inclusion Criteria:

1. Participant must have a total score of ≥ 16 on the HAM-A14 and ≥ 2 on both Hamilton Anxiety Rating Scale (HAM-A14) item 1 (anxious mood) and item 2 (tension) at screening and baseline [74] to be considered for inclusion into the study.
2. Participant is a primiparous new mother, 18-45 years inclusive, who had an uncomplicated vaginal or cesarean birth, gave birth to a healthy baby and both mother and baby are healthy at enrollment and randomization in the study.

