3. Sexually active female participants of childbearing potential must be self-report practicing, at least, one or more the following methods of contraception during the study: intrauterine device (IUD), barrier method in combination with a spermicide, oral/hormonal contraception or abstinence. Female participants of childbearing potential must have a negative urine pregnancy test before receiving study treatment.
4. Written informed consent must be obtained from the participant before study participation.
5. Participant is in good medical health.
6. No current abuse of alcohol or other substance.
7. Capable of giving informed consent.
8. Capable of doing active or sham CES treatments and completing all study requirements independently
9. For compliance, participants need to have completed 85% (36) of treatments to continue participation in the study

Exclusion Criteria:

1. Participant had complications during or after a vaginal or cesarean delivery.
2. Participant had multiple births.
3. Participant meets DSM-V criteria for a mental disorder diagnosis (i.e., schizophrenia, mood disorder, psychosis, anorexia nervosa) as determined by medical history and/or self-report.
4. Participant is clinically judged by the investigator to be at risk for suicide or is acutely suicidal. Participant has attempted suicide one or more times within the past twelve months.
5. Participant has a Hamilton Anxiety Rating Scale (HAM-A14) score above 30 which suggests a very severe clinical level of anxiety symptoms.
6. Participant has a Hamilton Depression Rating Scale (HAM-D17) score above 30 which suggests a very severe clinical level of depressive symptoms.
7. Participant has a psychiatric condition that would require inpatient or partial psychiatric hospitalization.
8. Participant has a significant history of medical disease (i.e. cardiovascular, hepatic (e.g., cirrhosis, hepatitis B or C) renal, gynecological, musculoskeletal, neurological (seizures), gastrointestinal, metabolic, hematological, endocrine, cancer with a metastatic potential or progressive neurological disorders) which could impair reliable participation in the trial or necessitate the use of medication not allowed by this protocol.
9. Participant is pregnant, planning to become pregnant. If a participant becomes pregnant, she will be dropped from the study immediately and followed appropriately.

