Instruments: See attached document entitled "Instrument Description" for detailed information related to this the scales referenced in this protocol.

The Hamilton Anxiety Rating Scale (HAM-A14)
Hamilton Depression Rating Scale¹⁷ (HAM-D17)
The Pittsburgh Sleep Quality Index (PSQI19)
The Insomnia Severity Index (ISI7)
The Barkin Index of Maternal Functions (BIMF20)

Recruitment and data collection is designed to fit into routine clinic procedures and scheduling and will be conducted in collaboration with clinic staff, administrators, and healthcare providers. Recruitment fliers briefly describing the study will be distributed by clinic staff in designated areas of the clinic. The PI or RA will conduct an information and training session with clinic staff. Potential participants who had uncomplicated vaginal or cesarean deliveries and healthy newborns will be told about the study by the clinic staff or health care provider .

If the new mother indicates interest in participating in the study, she will be asked to complete the background and demographic form and screening form (HAM-A14 item 1 (anxious mood) and item 2 (tension)). The clinic staff member will place the potential participant's completed materials in a sealed envelope and place in a locked file cabinet in an inner-clinic office within the clinic to be picked by the PI or RA weekly. The PI or RA will review the background and demographic form, screen the participant's responses against the inclusion/exclusion criteria, and review results of screening form. To enroll in the study, participants must score ≥ 2 on both HAM-A14 item 1 (anxious mood) and item 2 (tension) at screening and have a total score of ≥ 16 on the HAM-A14 at baseline. I included subjects with lower HAM-A14 scores than is typically used in GAD clinical trials (i.e. HAM-A14 > 20) since the subjects included will be a "healthy" population.

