The potential participant will be notified by the PI or RA if she qualifies for the study or does not meet the criteria for the study. If a new mother qualifies for the study, the PI or RA will briefly describe the study and time commitment. The PI or RA will explain the study's purpose and procedures and read the consent form to all potential participants. After the potential participant's questions are addressed and verbal consent to participate is obtained, the new mother will sign the informed consent form. If the new mother agrees to participate, an appointment will be scheduled at the participants' next scheduled clinic visit or at the current time and location with the PI or RA to complete Visit 1. Participants may also choose to complete study visits 1-3 during their current visit or at another designated location with the PI.

E(3). Incentives. If applicable, provide the amount, type, and time of distribution of any payment/incentive to participants.

All participants have the opportunity to receive a total of \$100.00 to compensate for their time:

Visit 1: \$40.00

Visit 2: \$20.00

Visit 3: \$40.00

Identification of Participants; Data Collection and Storage; Equipment; Records Retention

A. Identification of Participants. Indicate whether the data collected may contain individual identifiers (need for "confidentiality"), or whether the data will be collected anonymously.

Confidential

B. Data Collection. Describe the method(s) or procedure(s) for data collection **in step-by-step, layman's terms** (include collecting party, frequency, duration, location, etc).

The use of audio or video recording must be justified by the research purpose/objective or future research.

Participants will complete a daily 60 minute CES treatment and meet with the PI for three visits three weeks apart for a total of six weeks. Each visit will take approximately 60-80 minutes to complete.

• **Visit 1/First day of treatment**

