During study Visit 1 the PI or RA will explain the study and answer any questions. Participants will complete a urine pregnancy test. If the urine pregnancy test is negative baseline measures using the HAM-A14, HAM-D17, PSQI19, ISI7, and BIMF20 questionnaires will be completed by the participant with researcher assistance. Participants will then be given an Alpha-Stim® AID CES device kit with a serial number. The PI or RA will instruct participants on how to use the Alpha-Stim® AID CES device; then the participant will be asked to complete a 60-minute treatment. After the completion of the treatment, the participant will be asked about any side-effects or problems the participant may have experienced. Any side-effects information will be recorded on a side-effect form using the subject's words that describe what happened. The protocol for study treatments at home will be explained to you, and any questions will be answered. The participant will be reminded to complete your daily 60 minute CES treatment before the Visit 2 meeting. The participant will receive a \$40.00 Target Gift Card after Visit 1.

• **Visit 2**

At study Visit 2 The participant will be asked to complete a urine pregnancy test. If the urine pregnancy test is negative the participant will be asked to complete the HAM-A14, HAM-D17, PSQI19, ISI7, and BIMF20 questionnaires with researcher assistance. Your log will be reviewed and discussed. The participant will be asked about any side-effects that the participant may have experienced. The protocol for study treatments at home will be reviewed and the following device supplies will be given to you: six new AAA batteries and two 15ml. bottle conducting solution. The process of how to contact the PI or RA will be reviewed. The participant will be reminded to complete your daily 60 minute CES treatment before the Visit 3 meeting. The participant will receive a \$20.00 Target Gift Card after Visit 2.

• **Visit 3/ Last day of treatment**

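### Secondary objective 3 asks how well HAM-A14 items 1 and 2 screen for anxiety, but only screen-positive women receive the full scale, so sensitivity, specificity and NPV cannot be estimated

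*Protocol*

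**What the plan says.** Protocol, Purpose and Objective, item B, asks in its third secondary objective whether items 1 and 2 "on the 14 item Hamilton Anxiety Rating Scale (HAM-A14) perform well as a screening test for anxiety". The visible text names no reference measure for it.

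The procedures that would produce the data are these:

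- **Recruitment, E(2) Materials:** an interested woman fills in a background form and a screening form made up of HAM-A14 items 1 and 2 only: "she will be asked to complete the background and demographic form and screening form (HAM-A14 item 1 (anxious mood) and item 2 (tension". Entry then needs at least 2 on both items, with the total taken later: "item 2 (tension) at screening and have a total score of ≥ 16 on the HAM-A14 at baseline".
- **E(2), continued:** the woman "will be notified by the PI or RA if she qualifies for the study or does not meet the criteria for the study". The study description, consent and the Visit 1 appointment follow for those who qualify.
- **Data Collection, item B, Visit 1:** after a negative pregnancy test, "baseline measures using the HAM-A14, HAM-D17, PSQI19, ISI7, and BIMF20 questionnaires will be completed by the participant with researcher assistance". This is the first time the full HAM-A14 appears in the procedures.
- **Exclusion Criteria, item 5:** "Participant has a Hamilton Anxiety Rating Scale (HAM-A14) score above 30" is a reason for exclusion, so the total is limited at the top as well as the bottom.

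One passage reads differently. Inclusion criterion 1 sets the total of at least 16 together with at least 2 on "item 1 (anxious mood) and item 2 (tension) at screening and baseline [74] to be considered for inclusion into the study". Taken literally, that places the total at screening too.

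**The concern.** A screening test is judged against a reference obtained in both test-positive and test-negative people. Here the reference would be taken only in women who pass the screen. The false-negative and true-negative cells stay empty whatever the analysis.

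The entry rule makes the problem worse. If anxiety is defined by the same total of at least 16 that admits women to the trial, an analysis of enrolled women must find that every positive screen was correct. That would be reported as good performance although it is only the eligibility rule restated. The two items are also part of the total they are meant to predict, which favours agreement further.

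At stake is a misleading claim for a two-item screen. The comparison of active with sham stimulation is not touched.

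**Working it through.** The protocol states no accuracy target, sample size or result for this objective, so there is no figure to reproduce. The check is which cells of the 2×2 table the design can fill.

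**Inputs from the protocol.** Screen-positive means at least 2 on both items (E(2)). The entry total is at least 16 (E(2)), and totals above 30 are excluded (Exclusion Criteria, item 5). Planned enrolment is 50 (Participants, item C).

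**Assumptions.** The reference is a total of at least 16, the only cut-off for the presence of anxiety visible in the document. The numbers of women excluded at Visit 1 are not given, so a range is used.

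**Step 1: which cells are observed**

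| | Total ≥ 16 | Total < 16 |
|---|---|---|
| Screen-positive | TP: seen at Visit 1 | FP: seen at Visit 1, usable only if kept |
| Screen-negative | FN: never measured | TN: never measured |

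Sensitivity = TP/(TP+FN), specificity = TN/(TN+FP) and NPV = TN/(TN+FN) each need an unmeasured cell. Only PPV = TP/(TP+FP) does not. The gap in the lower row does not depend on the assumed reference, because no other anxiety measure is scheduled for screen-negative women.

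**Step 2: enrolled women only.** TP = 50 and FP = FN = TN = 0. Apparent sensitivity and PPV are both 50/50 = 100%; specificity and NPV are 0/0. A Wilson 95% interval for 50/50 is 93% to 100%, but it means little for a value fixed by the entry rule.

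**Step 3: all screen-positive women with Visit 1 scores kept.** Wilson 95% intervals are in brackets.

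| Women below 16 (assumed) | None above 30 | 10 above 30 (also reference-positive) |
|---|---|---|
| 10 | 50/60 = 83% (72–91%) | 60/70 = 86% (76–92%) |
| 25 | 50/75 = 67% (55–76%) | 60/85 = 71% (60–79%) |
| 50 | 50/100 = 50% (40–60%) | 60/110 = 55% (45–63%) |

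The same items read as 100% or as roughly 50% to 86%, depending only on whether excluded women are counted.

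**Step 4: how far the unmeasured row can move the answer.** Take 50 TP, 12 FP and 100 screen-negative women (all assumed), and let the share of screen-negative women with a total of at least 16 run from 0% to 30%:

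- Sensitivity: 50/50 = 1.00 down to 50/80 = 0.63.
- Specificity: 100/112 = 0.89 down to 70/82 = 0.85.
- NPV: 100/100 = 1.00 down to 70/100 = 0.70.
- PPV: 50/62 = 0.81 throughout.

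With 200 screen-negative women, sensitivity falls as far as 50/110 = 0.45. The observed scores are identical across each range.

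**Step 5: overlap of test and reference.** The two items supply at least 2 + 2 = 4 points, or 4/16 = 25% of the cut-off, for a woman who scores at least 2 on both at Visit 1.

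**The case against.** The strongest objection is inclusion criterion 1. If the total really is taken at screening, and from every woman screened, all four accuracy measures could be estimated. That reading cannot be ruled out from the criterion alone. But E(2) describes the form actually handed out, and it has two items. E(1) also ties the total to baseline. The operational steps support the finding, and the conflict itself needs correcting.

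Second, the reference may be named in the Instrument Description, to which the protocol refers the reader straight after the objective, or in an analysis plan. Neither is at hand. This limits the PPV figures, which rest on the assumed cut-off. It does not help with screen-negative women, for whom the visit schedule contains no anxiety measure of any kind.

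Third, which women enter an analysis is usually left to the analysis plan, and nothing says that forms of ineligible women are discarded. That is fair as far as PPV goes. The protocol does not say they are kept for this purpose either, and missing screen-negative scores are a gap in data collection.

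Fourth, the excluded-women counts are illustrative. They also leave out women excluded at Visit 1 for an item score below 2 or a HAM-D17 score above 30, some of whom would be reference-positive. This stands: the PPV range shows how the answer can move and is no forecast.

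Fifth, the objective is written for lay readers, and performing well could mean something looser, such as item–total association. HAM-A14 scores at Visits 2 and 3 do vary and would allow such statistics. They come from selected women using active or sham devices, so they say little about screening clinic attenders.

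**Conclusion.** The concern holds. Under the recruitment and Visit 1 steps, objective 3 cannot yield sensitivity, specificity or NPV, and no later analysis can repair that. PPV is the only one of the four that can be estimated, and only if Visit 1 scores are kept for screen-positive women who are then excluded. Restricted to enrolled women, the result is 100% by construction. With excluded women counted, it is about 50% to 86% in the scenarios shown.

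The unmeasured cells follow from the procedures in E(2) and Visit 1 alone. The percentages rest on an assumed reference (total of at least 16) and assumed exclusion counts. The point should be corrected. It concerns a secondary objective and leaves the primary comparison unaffected.

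**What to change.** Restate objective 3 along these lines:

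> Estimate, with a 95% confidence interval, the positive predictive value of HAM-A14 items 1 and 2 (both at least 2 on the clinic screening form) for a Visit 1 HAM-A14 total of at least 16. The population is all consented screen-positive women who complete the Visit 1 HAM-A14, including those then excluded for a total below 16 or above 30. Sensitivity, specificity and NPV are not assessed.

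The defined population also takes in women excluded at Visit 1 for another reason, such as an item score or HAM-D17; say so explicitly. State that the two items form part of the total, and add a sensitivity analysis relating them to the sum of the other 12 items in the same women. If a different reference is intended, name it in the objective. If none of this is wanted, drop the objective.

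Separately, reconcile inclusion criterion 1 with E(1) and E(2) on whether the HAM-A14 total is taken at screening or only at baseline.

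The cost is a wording change and the retention of some Visit 1 records from women who have already consented. Check that the consent form covers that use; it could not be checked here. The price is a narrower objective, with the overlap between items and total disclosed and examined but not removed. The change should be made before screening starts, because scores that were not kept cannot be recovered.

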At study Visit 3 The participant will be asked to complete a urine pregnancy test. If the urine pregnancy test is negative the participant will be asked to complete the HAM-A14, HAM-D17, PSQI19, ISI7, and BIMF20 questionnaires with PI or RA assistance. The subject's log will be reviewed and discussed as needed. The participant will be asked about any side-effects that the participant may have experienced. The Alpha-Stim® AID CES device and all supplies will be returned to the study team. The participant will receive a \$40.00 Target Gift Card after Visit 3.

C. Equipment. Describe any equipment to be used (e.g., audio, visual), ownership (e.g., TAMUCC, personal), and methods of storage (e.g., password, location).

Study Device: The Alpha-Stim® AID will be used for this study (Figure 1). The Alpha-Stim® AID is a prescriptive device and is FDA cleared for the treatment of anxiety, insomnia, and depression. About the size of a smart phone, the Alpha-Stim AID emits a mild electrical current via ear clip electrodes. The technical specifications for the Alpha-Stim® AID are shown on pages, 15-16. One-half of the devices will be active CES devices (0.5 Hz, 100 μ A (subsensory level), 50% duty cycle, biphasic asymmetrical rectangular waves) using ear clip electrodes. The other one-half of the devices (sham CES) will be identical to the active CES device except the ear clip electrodes will not emit electricity. The FDA has approved the device to be down classified from Class III to Class II (Federal Register, 2014). Subjects will complete a daily one hour CES treatment using ear clip electrodes (Figure 2.) with current set at fixed level of 100 μ A (subsensory level) for active CES treatment group for 6 weeks. The procedure will be the same for the sham group, but the Alpha-Stim® AID ear clips will not emit electricity.

Findings to date indicate that the Alpha-Stim® AID is an effective treatment with broad applications for a variety of syndromes for the management of anxiety, depression, and insomnia, or for the short-term relief of the symptoms of anxiety, depression and/or insomnia. In many cases it is the sole therapeutic method required.

Treatment Regimen:

The treatment regimen is one daily 60 minutes Alpha-Stim® CES treatment using ear clip electrodes for 6 weeks at 0.5 Hz, 50% duty cycle with a fixed current of 100 μ A (subsensory level). The sham CES unit is identical except the sham ear clip electrodes do not emit electricity.

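### Inclusion item 9 (36 of 42 sessions) is a post-randomisation retention rule listed among the eligibility criteria; its timing is undefined, it conflicts with the visit text, and it can cost outcome data

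*Protocol*

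**What the plan says.** All references are to the protocol.

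- **Participants, part B, Screening and Inclusion Criteria, item 9:** "For compliance, participants need to have completed 85% (36) of treatments to continue participation in the study".
- **Heading of part B**, under which the item stands: "Describe the criteria to determine who is included or excluded in the final participant population".
- **Recruitment, E(2):** before Visit 1 the PI or RA is to "screen the participant's responses against the inclusion/exclusion criteria".
- **Data Collection, part B, Visit 1:** after the baseline measures, "Participants will then be given an Alpha-Stim® AID CES device kit with a serial number". The first session follows at that visit and the rest are done at home: "The participant will be reminded to complete your daily 60 minute CES treatment before the Visit 2 meeting".
- **Visit 2:** the questionnaires are asked for if the pregnancy test is negative; then "Your log will be reviewed and discussed".
- **Visit 3, last day of treatment:** again the questionnaires depend only on the pregnancy test, and afterwards "The subject's log will be reviewed and discussed as needed".
- **Spacing:** participants "meet with the PI for three visits three weeks apart for a total of six weeks".

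Two other rules lie close by. Exclusion item 11 covers poor compliance, partly by investigator judgment and without a time limit. The section on assigning subjects to groups gives a dropout's device to her replacement. Neither mentions item 9.

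**The concern.** An eligibility criterion should be decidable before allocation. This one depends on what a woman does with an allocated device over six weeks. Applied as a condition for continuing, it selects on behaviour after randomisation.

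The primary objective is the effect of CES on anxiety, compared with sham. If adherence relates to outcome differently in the two arms, women who pass the rule are no longer comparable between arms. If the rule stops a woman before Visit 3, her final outcomes do not exist and no analysis plan can restore them. That is why the point does not depend on the analysis plan that is not shown.

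The text also leaves staff with two instructions that disagree: item 9 ties continued participation to adherence, while the visit descriptions tie the assessments to the pregnancy test alone.

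**Working it through.** **1. The plan's own figure.** One session daily for six weeks: 7 × 6 = 42. 0.85 × 42 = 35.7, rounded up to 36. Check: 36/42 = 85.7% and 35/42 = 83.3%. The stated 36 is reproduced. Allowed misses: 42 − 36 = 6, so the seventh miss puts 36 out of reach.

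**2. When the rule can act.**

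| Point | Sessions possible | What item 9 can do |
|---|---|---|
| Screening, before Visit 1 | 0 | Cannot be judged |
| Visit 2, about week 3 | about 21 | Nobody can have reached 36; acts only through an unstated reading |
| Visit 3, last treatment day | about 42 | Count of 36 can be checked; little participation is left to continue, so the effect would be removal from the final population |

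Two unstated readings are open at Visit 2:

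- futility: 7 or more misses, so 36 is unreachable;
- pro rata: 0.85 × 21 = 17.85, so fewer than 18 of 21 fails.

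**3. How many women (illustration).** The protocol gives no adherence data. Assume home sessions are missed independently with daily probability q. The first session is done at Visit 1, so there are 20 to 21 home sessions by Visit 2 and 41 in all. The shares are binomial tails: P(7 or more misses) for futility and for the final count, P(4 or more misses) for pro rata.

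| q | Visit 2, futility | Of 50 women | Visit 2, pro rata | Below 36 by the end |
|---|---|---|---|---|
| 10% | 0.2–0.3% | 0.1–0.2 | 13–15% | 11% |
| 15% | 2–3% | 1.1–1.4 | 35–39% | 42% |
| 20% | 9–11% | 4.3–5.4 | 59–63% | 74% |

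If misses cluster within women (beta-binomial, assumed within-woman correlation 0.1), the futility shares at Visit 2 become 5–6%, 11–13% and 20–22%.

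**4. What selection could do (illustration).** Let a share f of least adherent women be removed in each arm, and let adherence correlate with outcome at ρ in one arm only. With no true effect, the bias in SD units is ρ × φ(z_f)/(1 − f), where z_f is the standard normal f-quantile. Worked case, f = 9% and ρ = 0.5: 0.5 × 0.1624/0.91 = 0.089. Type I error is from simulation: 100,000 runs, t-test, 25 per arm, no replacement.

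| f | Bias, ρ = 0.5 | Bias, ρ = 0.3 | Type I error, ρ = 0.5 |
|---|---|---|---|
| 2% | 0.025 | 0.015 | 5.1% |
| 9% | 0.089 | 0.054 | 6.1% |
| 11% | 0.106 | 0.063 | 6.4% |
| 20% | 0.175 | 0.105 | 8.6% |

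With the same selection in both arms, bias is 0.00 SD and type I error stays at about 5%. The table covers shares up to 20%; it does not model the 42% or 74% that could fall below 36 by Visit 3.

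**5. Numbers.** Participants, part C recruits 50 against 44 needed, so 50 − 44 = 6 losses from all causes are covered. This matters only if removed women are not replaced.

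**The case against.** The best defence has four parts.

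- **No visit orders a removal.** Visits 2 and 3 contain no such step, and nobody can have completed 36 sessions by week 3. A reader might infer that the protocol, followed as written, withdraws women at Visit 2. It does not say so; that needs the futility or the pro rata reading, neither of which is stated. This stands, and the Visit 2 route is put forward only as an inference.
- **Analysis sets belong to the analysis plan.** At Visit 3 the questionnaires come before the log review, so the data would exist and a plan could keep them. The phrase about the final population is the IRB form's prompt, not an analysis-set definition. This stands in part: removal at Visit 3 is possible, not prescribed. But item 9 is the investigator's own answer to that prompt, and no sentence keeps non-adherent women in follow-up.
- **The harm is assumed.** Miss rates, the correlation and its confinement to one arm are all assumptions. The current is subsensory, and participants, PI and RA are blinded, so similar selection in both arms is plausible. A reader might infer from the tables that the trial will be biased or its type I error inflated; the document does not support that.
- **Exclusion item 11 and the replacement rule do not name item 9.** Correct. They cannot be counted as further removal rules and need only be reconciled with it.

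What the defence leaves untouched is the misplacement, the undefined timing and the conflict with the visit text.

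**Conclusion.** The point holds, as something that should be fixed. It is certain from the text that item 9 is a condition on post-randomisation behaviour, that it sits in a list applied before any session has taken place, and that it disagrees with the visit descriptions. Removal from the final population at about Visit 3 is a possible consequence of the wording. Loss of Visit 3 outcomes after the Visit 2 log review is a further possibility, by inference.

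The size and direction of any bias are unknown. Under independent misses at 10% to 20% per day, the futility reading would put 0.1 to 5.4 of 50 women at risk of losing Visit 3 data; clustering of misses or the pro rata reading would raise this. Bias is near zero if selection is alike in the two arms. In the worst case tabulated (20% removed, correlation 0.5 in one arm only) it is about 0.17 SD, and nothing in the blinded design points to that case.

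**What to change.** 1. Move item 9 out of the eligibility criteria.
2. State that falling below 36 sessions does not end study assessments: every randomised woman is asked to complete the remaining questionnaires through Visit 3, subject to the existing pregnancy rules and withdrawal of consent, and is not removed from the randomised population.
3. Use 36 of 42 only to describe adherence or to define a supplementary per-protocol set.
4. Reconcile exclusion item 11 and the replacement rule with this, so that neither is read as taking randomised women out of follow-up for low adherence.

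No change to treatment or to the handling of pregnancy is proposed.

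The cost is an IRB wording amendment and a few extra Visit 3 assessments, meaning staff time and the 40-dollar gift card per woman. Visit 2 adds nothing, because its questionnaires come before the first scheduled log review. Keeping non-adherent women will dilute the estimate somewhat.
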